6.1. Disposition

A listing of randomisation information (including randomisation and kit number) for all randomised subjects will be produced.

Subject disposition will be summarised for the following categories: subjects in the All Enrolled, FAS, PP Set and Safety Set. A disposition of subjects includes the number and percentage of subjects who were enrolled, subjects that were screening failures, subjects randomised and subjects who completed the study, subjects who discontinued from the study, and subjects that were unblinded during the study. The number of subjects will be displayed by treatment group and overall, except screening failures where counts will only be displayed in the overall group. The reasons for study discontinuation may include any of

the following: Lost to Follow-up, Subject withdraws consent, Death, Adverse event, Physician decision, Pregnancy, Protocol violation, Study terminated by the Sponsor, and Other. The reasons for study discontinuation will also be summarised in this table. The percentages will be based on the number of subjects randomised.

Disposition data, displaying both randomised and actual treatment in case of randomised/treated subjects, will be listed, for all enrolled set.

6.2. Protocol Deviations

Major (relevant) protocol deviations will be identified and confirmed prior to database lock and summarised by the deviation categories shown in study deviation rules document.

The major protocol deviations will be summarised for the FAS and includes the number and percentage of subjects who had each major deviation. Subjects can have more than one type of major deviation. Percentages will be based on the total number of subjects in the FAS.

Protocol deviations (including minor deviations) will also be presented in a listing. A flag (Y/N) will be added to the listing to denote whether a subject is included or excluded from the PP Set.

7. Demographics and Baseline Characteristics

7.1. Demographics

A summary of demographics and baseline information will be presented for the Safety and Full Analysis Sets. The demographic characteristics consist of age (years), sex (Female, or male), race (Caucasian, Asian, African, Indian, or Mixed/Other), smoking and alcohol use.

Age (years) will be summarised using descriptive statistics. The number and percentage of subjects by sex, race, smoking and alcohol consumption will also be reported. Percentages will be based on the total number of subjects in the specific analysis set being summarised (Safety Set or Full Analysis Set as applicable).

7.2. Baseline Disease Characteristics

The following baseline disease characteristics of PD history, Mini-mental State Examination (MMSE), and duration of PD, will be summarised for the Safety and Full Analysis Sets (FAS), as recorded on the “Demography” and “Mini-mental State Examination (MMSE)” eCRF pages. MMSE score and duration of PD will be summarised using descriptive statistics. The number and percentage of subjects by PD history by Hoehn and Yahr stage and MMSE score category: abnormal (severe (≤ 9 points), moderate (10-18 points), mild (19-23 points)) and normal (≥ 24 points), and the number and percentage of duration of PD category (<5 years, 5-10 years, and >10 years), will also be reported. Percentages will be based on the total number of subjects in the specific analysis set being summarised).

Subject demographic and baseline characteristics will be listed for all patients enrolled in the study, including screen failures

7.3. Medical History

Medical history will be coded using the Medical Dictionary for Regulatory Activities (MedDRA) Version 21.0. The primary system organ class (SOC) and preferred term (PT) will be coded according to the Lower Level Term (LLT). The number and percentage of subjects with any medical history will be summarised overall and for each SOC and PT. Percentages will be calculated based on number of subjects in the Safety Set.

This summary will be presented in alphabetical order for the SOC. Within each SOC, the PTs will be presented by descending order of frequency.

Subject medical history data will be presented for the Safety Set in a listing.

7.4. Inclusion and Exclusion Criteria

Inclusion and exclusion criteria for eligibility for participation in the study are listed in sections 5.1 and 5.2 of the study Protocol. Subjects including screen failure subjects along with the inclusion/exclusion criteria will be listed for all subjects enrolled.

8. Prior and Concomitant Medications

All medications or vaccine (including over-the-counter or prescription medicines, vitamins, and/or herbal supplements) that the subject is receiving at the time of enrollment or receives during the study, will be collected on the eCRF. All medications will be coded according to the World Health Organization Drug Dictionary Enhanced (WHODDE, March 2018). In addition, the Anatomical Therapeutic Chemical (ATC) classes are assigned to the drug code for Anti-Parkinson Treatment Prior and Concomitant Medication, and Level 4 of the ATC coding and PT is required.

For summary purposes, medications will be considered prior medications if they stopped prior to the first dose of study drug and concomitant medications if they were taken at any time on and after the first dose of study drug (i.e. started prior to the first dose of study drug and were ongoing or started on and after the first dose of study drug).

For the purpose of inclusion in prior and/or concomitant medication tables, incomplete medication start dates and end dates will be imputed as follows:

- If year and month are present and day is missing, then set day to first day of month for start date, and set day to last day of month for end date
- If year and day are present and month is missing, then set month to January for start date, and set month to December for end date
- If year is present and month and day are missing, then set month and day to January 1 for start date, and set month and day to December 31 for end date

- Completely missing dates will not be imputed

If start date is completely missing and end date is not prior to the first dose, then the medication will be classified as concomitant. If the start date is completely missing and end date is prior to the first dose of study drug, then the medication will be classified as prior. If the end date is missing, then the medication will be classified as ongoing.

8.1. Prior Medications

The total number of prior and concomitant medications, as reported on the “Concomitant Medications” eCRF page (identified based on start date in relation to first dose date), the number and percentages of subjects using each type of prior and concomitant medication, and the number and percentages of subjects with at least one prior and concomitant medication,), will be summarised by treatment group and listed by ATC level 4 category, and PTs.

Anti-Parkinsonian Prior and Concomitant medication as reported on “Anti-Parkinsonian Prior and Concomitant” eCRF page will be defined in a similar way as for Prior and Concomitant Medication.

These will be presented in a single summary table.

These summaries will be presented in descending order of frequency, by ATC level 4 category. Likewise, within each ATC level 4 category, preferred terms will be presented by descending order of frequency.

All summaries and listings will be performed using the Safety Set.

8.2. PRN Medications

The total number of PRN PD pain medications, the number and percentages of subjects using each type of PRN PD pain medication, and the number and percentages of subjects with at least one intake of PRN PD pain medication as reported on the “PRN Parkinson’s Disease Pain Medication” eCRF page, will be summarised by treatment group and listed by ATC4 category, and PT. All summaries and listings will be performed using the Safety Set.

9. Exposure and Compliance

9.1. Exposure to study treatment

In case an additional kit is obtained to replace the Randomization Kit that might have been lost or damaged, Investigator shall initiate an unscheduled dispensation. A listing of subjects’

unscheduled dispensing, as recorded in “Unscheduled Dispensation” eCRF page will be produced for the Safety Set.

9.2. Study compliance

Study medication accountability and subject compliance will be documented throughout the treatment period, using study-specific study medication dispensing and return record forms, and will be reported in ‘Drug Accountability’ eCRF page. The eCRF does not collect exposure data in a fashion that enables to calculate compliance, only investigator’s assessment result for compliance is collected by visit as Yes or No. Compliance categories of “Yes” or “No” indicate that the patients took at least 80% of the study medication during any visit- to- visit evaluation Period “Yes” and non-compliance is defined as taking less than 80 % of study medication “No”.

Complete data about study medication accountability and subject compliance will be presented in a listing.

10. Efficacy Analysis

The primary analysis of the efficacy endpoint will be performed for the FAS and in case there is a difference of more than 10% between FAS & PP, will be repeated on the PP Set as a sensitivity analysis.

Secondary efficacy endpoints will be analysed for the FAS population at Week 4,8 and 16.

Data listings will be provided for all endpoints. An additional listing of diary collection status by visit, as reported in “Questionnaire Collection Status -Baseline”, “Questionnaire Collection Status”, and “Questionnaire Collection Status – V5 EoT WK16” eCRF pages, will be presented.

10.1. Primary Efficacy Endpoint

Pain severity data will be derived from the daily diary.

The primary endpoint evaluated in this study is the mean change in pain severity (“average worst pain experienced in the last 7 days”, i.e. average of the worst pain score on each of the 7 days preceding the site visit), as assessed by an 11-point NRS, from baseline to Week 16. For efficacy analysis, at least 4 out of 7 daily pain scores are needed to calculate a valid average over 7 days.

The null hypothesis for the primary endpoint is that safinamide is no better than placebo in managing pain; thus $\mu(\text{Safinamide}) > \mu(\text{Placebo})$, where μ represents the population mean change in pain severity score from baseline at Week 16 and a negative change would indicate improvement.

The primary efficacy endpoint, change from baseline to Week 16 in pain severity score, will be analysed using a mixed model repeated measures (MMRM) using visit on subject ID as

the repeated factor with unstructured covariance term (REPEATED VISIT/SUBJECT=SUBJID TYPE=UN). If convergence is not achieved, then other covariance structures will be investigated such as compound symmetric (TYPE=CS). The model will include fixed effects terms for treatment, country, visit and regular pain medication use at baseline (yes or no) and covariate term for pain severity score at baseline. The method above (e.g. MMRM) is unbiased under the MAR assumption and can be thought of as aiming to estimate the treatment effect assuming that after withdrawal, subjects would have continued on a similar trajectory to their peers in the same arm who have the same covariates.

The likelihood-based mixed-effect model repeated measure will be performed using a SAS PROC MIXED procedure, and the Kenward-Roger method for degrees of freedom will be applied. The restricted maximum likelihood (REML) method will be used for estimation. The least square (LS) means of change from baseline in pain severity along with the associated SE and 95% CIs will be calculated from the model at each time point. The LS mean difference between the treatment groups at Week 16 will also be reported, along with the corresponding SE, 95% CIs, and the p-value derived for the difference between treatment arms (safinamide – placebo). No adjustment is being made for multiple comparisons.

Results for time points other than Week 16 (Weeks 4 and 8) will be presented in both the above discussed model-adjusted and descriptive forms.

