3.1. Overall Study Design and Plan

This is a Phase IV, international, multicentre, randomised, double-blind, placebo-controlled study in IPD male and female subjects 30 years of age or older, experiencing motor fluctuations and PD related chronic pain while on stable doses of L-Dopa. The duration of the study for each subject is 19 weeks (including the Screening period). Subjects will be randomised to receive either active or placebo in a 2:1 ratio, respectively. A telephone follow-up call will be performed 1 week after the end of treatment.

[figure not shown]
Study consists of two periods, screening (1-2 weeks) and a treatment period (16 weeks), with a follow-up call at 1 week after treatment, so total duration of 19 weeks.

The Screening visit (Visit 1) should occur up to 14 days before Day 1. At baseline (Visit 2, Day 1), eligible subjects will enter the treatment period and will receive study medication 50 mg (from Day 1 to Day 7) and then 100 mg (from Day 8 onwards), to be taken orally once daily (od). Following completion of all baseline assessments, they will receive the first dose of study medication at the study centre. Thereafter, study drug will be taken, at home, each morning along with their first morning dose of L-Dopa and other (if any) PD medications. On Day 8 the dose of study drug will be increased, at home, to 100 mg od. Each subject will receive treatment for 16 weeks, with visits at Week 0/Day 1 (baseline) and at Weeks 4, 8 and 16 (or early termination).

From day 1 onwards, participant will record the use of PRN medications along with indicating the worst pain experienced on a daily basis.

Diagram of Study Schedule:

Figure 1: Diagram of Study Schedule

Randomisation is in a 2:1 ratio of active:placebo; up to 132 participants will be screened to achieve up to 105 randomized, to have approximately 84 patients complete the study (56 in the active and 28 in the placebo group respectively). The detailed description is present in [Section 4.1](#).

Subjects will take their allocated study drug in accordance with the assigned regimen:

Safinamide: 50 mg (from Day 1 to Day 7) and then 100 mg (from Day 8 onwards)
or
Placebo: 50 mg (from Day 1 to Day 7) and then 100 mg (from Day 8 onwards)

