4.1. Sample Size

On the basis of previous post-hoc analyses of pain (Cattaneo et al 2017) and of similar studies ([Folstein et al, 1975](#)), assuming a standard deviation of 2 it is anticipated that a sample size of 144 subjects would permit detection of a 1 point treatment difference in the NRS between safinamide and placebo at the 5% significance level with 80% power. A 1-point treatment difference is considered to be a clinically meaningful treatment effect ([Rascol et al, 2016](#)).

Approximately 220 subjects will be screened to achieve approximately 177 randomly assigned to study treatment and of which approximately 144 subjects completing the study (n= 96 and n= 48 evaluable subjects in the active and placebo group respectively).

Since March 2020, the COVID-19 emergency has impacted the feasibility of the trial, which is being conducted in a vulnerable group of patients. Upon receipt of the guidance “Statistical Considerations for Clinical Trials During the COVID-19 Public Health Emergency” issued by FDA on June 2020, released with the aim of helping sponsors ensure that trials conducted during the Covid-19 emergency could continue, where appropriate, to provide interpretable findings with correct statistical quantification of uncertainty, the Sponsor performed a Blind Data Review Analysis of the primary endpoint data (pain severity) for the 26 patients who had completed the study as of June 2020.

The results of the analysis show that the standard deviation used in the original sample size estimation (SD = 2) was a conservative overestimate of the observed SD from the actual trial data, which was 1.43 at the time of the blinded data review.

Based on this, the Standard Deviation, for the estimation of sample size has now been amended to 1.50, and the power has been maintained as 80%. New sample size estimates have been performed considering different magnitudes of Treatment Difference but keeping

the same assumptions of screen failure rates and dropout rates. These are summarized below in [Table 4.1](#).

Table 4.1 Sample Size Estimations

SCENARIO	SAMPLE SIZE
Power = 80% Standard deviation = 1.5 Treatment Difference = 1 point	Pts to screen= 132 Pts to randomize= 105 Pts completing study= 84
Power = 80% Standard deviation = 1.5 Treatment Difference = 1.5 points	Pts to screen= 66 Pts to randomize= 51 Pts completing study= 39

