10.2. Sensitivity of Primary Endpoint

The following two sensitivity analyses will be performed:

- a) This sensitivity analysis will be based on the PP Set, and the primary endpoint (mean change pain severity as assessed by an 11-point NRS, from baseline to Week 16), will be analysed using similar MMRM approach as specified in [Section 10.1](#). No imputation will be performed in this analysis.
- b) This sensitivity analysis will be based on the FAS population. Missing records of subjects who prematurely discontinued the randomly assigned study drug, will be imputed with the worst value from baseline before drop out within each subject. Intermittent missing data will not be imputed and all missing values after discontinuation will be imputed. The worst value is the highest pain score from baseline to before drop out. Change from baseline for the imputed Week 16 value will then be calculated as imputed Week 16 - baseline. For example in the following case:

3 1 x 2 3 y y

where x and y are missing data, the imputation will complete y values but not x as it is the intermittent missing data.

The primary endpoint (mean change in pain severity as assessed by an 11-point NRS, from baseline to Week 16), will be analysed by using a repeated measures analysis

of covariance (ANCOVA) for the imputed population, using visit on subject ID as the repeated factor with unstructured covariance term (REPEATED VISIT/SUBJECT=SUBJID TYPE=UN). If convergence is not achieved then other covariance structures will be investigated such as compound symmetric (TYPE=CS). The model will include fixed effects terms for treatment, country, and visit, and covariate term for pain severity score at baseline.

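### The primary MMRM has no treatment-by-visit term, so its Week 16 difference is a weighted average over Weeks 4, 8 and 16

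*SAP*

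**What the plan says.** **Target.** SAP 10.1 states the null hypothesis in terms of μ, "where μ represents the population mean change in pain severity score from baseline at Week 16". Treatment-phase assessments are scheduled "with visits at Week 0/Day 1 (baseline) and at Weeks 4, 8 and 16 (or early termination").

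**Model.** The same section specifies an MMRM with an unstructured covariance over visits ("REPEATED VISIT/SUBJECT=SUBJID TYPE=UN") and then lists the mean structure: "The model will include fixed effects terms for treatment, country, visit and regular pain medication use at baseline (yes or no"), with baseline pain as covariate. Protocol 9.4.1 has the identical list. Neither document mentions a treatment-by-visit interaction anywhere.

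**Promised output.** LS means by arm "will be calculated from the model at each time point". In addition, "The LS mean difference between the treatment groups at Week 16 will also be reported", with SE, confidence interval and p-value. SAP 10.1 also promises model-adjusted results for Weeks 4 and 8.

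**Other models.** Sensitivity analysis (b) in SAP 10.2 has its own list: "The model will include fixed effects terms for treatment, country, and visit, and covariate term for pain severity score at baseline". It too has no interaction, and it omits regular pain medication use. Sensitivity analysis (a) and the SAP 10.3 analyses of PGI-C, CGI-C, CGI-S, MDS-UPDRS and pain at Weeks 4 and 8 reuse the primary model.

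**The concern.** With treatment and visit as main effects only, the fitted arm profiles are parallel. The treatment difference at Week 16 is forced to equal those at Weeks 4 and 8. The unstructured covariance does not relax this: it sets the weights of the average, not the shape of the means. The listed terms therefore cannot deliver the Week 16 contrast that the SAP names.

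The primary p-value and confidence interval are at stake. If the effect builds over time, the estimate is diluted, and with a steep enough build-up power falls. If the effect fades, the trial can declare a Week 16 benefit that is not there. The Week 4 and Week 8 pain analyses would simply repeat the primary result.

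**Working it through.** **1. The plan's sample size.** Inputs from SAP 4.1: difference 1, SD 1.5, 2:1 allocation, 56 + 28 completers, "at the 5% significance level with 80% power". The significance level is taken as two-sided because that reproduces the plan's figure.

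- SE = 1.5 × √(1/56 + 1/28) = 0.347, and 1/0.347 = 2.88.
- Power is 81% (noncentral t) or 82% (normal approximation).
- The t-based calculation gives exactly 84; one-sided 5% would give 63.
- 84/0.80 = 105 randomised.

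The sample size is thus built for one two-group comparison with SE 0.347, which is what a Week 16 contrast provides.

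**2. What the listed model estimates.** Let d be the vector of true treatment differences at Weeks 4, 8 and 16 (pain reductions shown as positive) and S the 3 × 3 covariance over visits. With complete data and one common treatment coefficient, generalised least squares estimates w′d, where

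- w = S⁻¹1 / (1′S⁻¹1)
- SE = √[(1/56 + 1/28) / (1′S⁻¹1)]

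Rejection probability at two-sided 5% is Φ(q − 1.96) + Φ(−q − 1.96), with q = |w′d|/SE. The time-fixed covariates are left out of this approximation.

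**3. Assumptions.** The documents give neither S nor d. I used correlations of 0.5, 0.6 and 0.7 common to all visit pairs (compound symmetry), and a decaying pattern: 0.7 between adjacent visits and 0.5 between Weeks 4 and 16. SDs were either 1.5 throughout or rising (1.2, 1.35, 1.5).

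**4. Weights and standard errors.**

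- Equal SDs, compound symmetry: weights 1/3 each. The variance factor is 2.25 × (1 + 2ρ)/3, which is 1.5 at ρ = 0.5 and 1.8 at ρ = 0.7. Multiplying by 0.0536 and taking the root gives SE 0.283 to 0.311.
- Equal SDs, decaying: weights 0.43/0.14/0.43, SE 0.299.
- Rising SDs: Week 4 carries 53–67% of the weight and Week 16 only 4–24%.

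**5. Results with equal SDs.**

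| True effect, Weeks 4/8/16 | Common-effect estimate | Rejection, listed model | Rejection, Week 16 contrast |
|---|---|---|---|
| 1 / 1 / 1 | 1.00 | 90–94% | 82% |
| 0.8 / 0.9 / 1.0 | 0.90 | 83–89% | 82% |
| 0.4 / 0.7 / 1.0 | 0.70 | 62–70% | 82% |
| 0 / 0.5 / 1.0 | 0.50 | 36–42% | 82% |
| 0.8 / 0.5 / 0 | 0.41–0.43 | 28–33% | 5% |
| 1 / 1 / 0 | 0.57–0.67 | 48–65% | 5% |

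One cell in full (third row, ρ = 0.5): (0.4 + 0.7 + 1.0)/3 = 0.70; 0.70/0.2835 = 2.47; Φ(2.47 − 1.96) = 0.695.

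With the rising SDs, the 0.8/0.5/0 profile is rejected in 60–72% of trials.

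**6. Simulation.** With complete data, equal SDs and the decaying correlation (4,000 trials per case), 0/0.5/1.0 gave a mean estimate of 0.50 with 40% rejection, and 1/1/0 gave 0.58 with 49%. The Week 16 contrast rejected in 81% and 5% respectively. A smaller run (600 trials, 105 randomised, about 22% monotone dropout) gave 0.66 with 65% power for 0.4/0.7/1.0, and 37% rejection for 0.8/0.5/0. Dropout moves weight towards the early visits.

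**The case against.** The strongest reply is that the SAP fixes its target repeatedly: the endpoint, the null hypothesis, LS means by visit, a named Week 16 difference, and separate Week 4 and 8 results. Those outputs make sense only with an interaction, so the term list may simply be incomplete. The table shells, which are not part of these documents, might show this. That is a fair reading of intent, but it does not supply the term. Three separate lists omit it, and SAP section 12 records no such change. A programmer following the text would fit the main-effects model. Adding the term later would be an undocumented choice on the primary test.

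Second, the harmful profiles are assumptions. The dose is constant from Day 8, so all three visits fall on the same dose and a plateau is possible. With a flat or nearly flat profile the listed model has more power than the Week 16 contrast, as the first two table rows show. This stands: power is lost only when the build-up is steep enough. But the documents neither assume nor justify a constant effect. Protocol 6.5 requires regular analgesics to stay stable only for at least the first 4 weeks, so background treatment may change between Weeks 4 and 16.

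Third, a missing baseline-by-visit term does not prevent estimation of a Week 16 contrast, and the covariate missing from SAP 10.2(b) is a separate inconsistency. Both points are right, and both changes are secondary.

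**Conclusion.** The primary model is wrong as written. That its Week 16 difference is the common effect over Weeks 4, 8 and 16 is algebra and needs no assumption. It answers the stated hypothesis only if the effect is constant across visits.

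The size of the error is illustrative, because visit correlations, visit SDs and effect profiles are all assumed. Under equal SDs it ranges from no bias with a power gain (constant effect) to roughly half the Week 16 effect and 36–42% power (0/0.5/1.0). When the benefit has gone by Week 16, false rejection is several times the nominal 5%, and it is higher still if SDs rise over visits. The sample size of 84 completers is not affected.

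**What to change.** Essential, before database lock:

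- Add treatment-by-visit to the fixed effects in SAP 10.1 and Protocol 9.4.1.
- State that the primary test is the Week 16 treatment contrast from the treatment-by-visit LS means.
- Put the same term in SAP 10.2(b). Sensitivity analysis (a) and the SAP 10.3 models then inherit it from 10.1.

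Advisable at the same time:

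- Add baseline-by-visit.
- Restore regular pain medication use in SAP 10.2(b), or explain its absence.

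The cost is a line of wording, one essential model term and a few degrees of freedom. If the effect really is constant, the SE rises from about 0.28–0.31 to 0.35 and power for a 1-point effect falls from 90–94% to 82%. That is the precision the sample size was planned on, so the numbers to randomise and complete stay at 105 and 84.
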